7.12 Reproductive Hormone Assessments

Reproductive hormone levels will be measured in all subjects. Blood samples will be collected to assess FSH, LH, estradiol, and progesterone in females, and FSH, LH, and testosterone in males.

7.13 Safety Assessments

7.13.1 Physical Examination

Physical examinations will include a review of the subject's general appearance as well as evaluation of the body systems. Any clinically significant abnormal change in findings will be recorded as an AE on the appropriate CRF. The physical examination will include the following:

- General appearance
- Eye, ears, nose, throat
- Lymph nodes
- Cardiovascular
- Skin
- Abdomen
- Neurological
- Spine and extremities
- Lungs

7.13.2 Vital Signs

Vital signs are to be recorded for all subjects and will include pulse, blood pressure, respiration rate, and temperature.

7.13.3 Electrocardiography

A standard 12-lead ECG will be performed after 10 minutes at rest when the patient is seated or supine following treatment. ECG results will be read locally at the clinical site. Abnormalities will be recorded.

7.13.4 Clinical Laboratory Tests

Blood and urine samples will be collected as described in this section for clinical laboratory testing. The clinical laboratory tests to be performed are listed in [Table 7-1](#).

Table 7-1 List of Clinical Laboratory Tests

Hematology:	Serum Chemistry:
- Hematocrit	- Albumin
- Hemoglobin	- Alkaline phosphatase
- Mean corpuscular hemoglobin	- Alanine aminotransferase
- Mean corpuscular hemoglobin concentration	- Aspartate aminotransferase
- Mean corpuscular volume	- Calcium
- Platelet count	- Carbon dioxide
- Red blood cell count	- Chloride
- White blood cell count with differential	- Creatinine
	- Creatine kinase
	- Gamma-glutamyl transferase
	- Glucose
	- Lactate dehydrogenase
	- Phosphorus
	- Potassium
	- Sodium
	- Total bilirubin
Urinalysis*:	
- Appearance	
- Bilirubin	
- Color	
- Glucose	
- Ketones	
- Nitrite	
- Occult blood	
- pH	
- Protein	
- Specific gravity	

*Urinalysis will not be conducted for subsequent attacks.

7.13.5 Local Tolerability

Injection site reactions (erythema, swelling, burning sensation, itching/pruritus, warm sensation, cutaneous pain, or other) will be evaluated by the investigator or other medically qualified personnel, the home healthcare provider, or the parent/legal guardian/caretaker after having received appropriate training, and the diameter of any erythema or swelling will be measured.

After discharge or in a subject treated at home for a subsequent attack, the subject (or the subject's parent/legal guardian on behalf of the subject as appropriate) will report about injection site reactions, either in person or by telephone contact.

7.13.6 Immunogenicity

The immunogenicity of icatibant will be assessed. Serum samples for immunogenicity testing will be collected for determination of anti-icatibant antibodies. Serum samples will be analyzed for anti-icatibant antibodies at Shire or at a designated laboratory. Details concerning sample collection and preparation will be provided in the study Laboratory Manual.

Samples will be stored frozen at -65°C or below if not shipped on the day of collection. Details for shipping will be provided in the study Laboratory Manual.

7.13.7 Pregnancy Testing

Female subjects of childbearing potential (ie, those who have experienced menarche) will undergo pregnancy testing at time points specified in the study schedule of events ([Appendix 1](#), [Appendix 2](#), and [Appendix 3](#)). All pregnancy testing will be conducted using a urine human chorionic gonadotropin (hCG) test kit. The test will be performed and interpreted prior to study drug administration.

7.14 Sample Collection, Storage, and Shipping

Blood samples will be collected via venipuncture. Use of an indwelling catheter is encouraged for collection of serial blood samples for PK assessments when feasible. Use of a topical local anesthetic (such as EMLA or LMX) is acceptable to make the procedure more tolerable for children, provided that the timing of this application does not interfere with blood sample collection. Subjects will be in a seated or supine position during blood collection.

All samples will be stored and secured in a way that assures that unauthorized access is prohibited and the samples are not lost, allowed to deteriorate, or are accidentally or illegally destroyed. Detailed sample collection, processing, and shipping instructions will be provided in the study Laboratory Manual.

7.15 Recording of Concomitant Medications

All medications administered to the study subjects from the time of informed consent through the final follow-up visit 90 (± 7) days after investigational product administration are regarded as concomitant and will be documented in the CRF. Concomitant medications are defined in [Section 6.6](#).

7.16 Recording of Adverse Events

Adverse events will be collected over an observation period from the time of treatment until the final follow-up visit 90 (± 7) days after investigational product administration (or until the event has resolved/stabilized or an outcome is reached, whichever comes first). Adverse event monitoring and the period of observation defined for this study are described in Section 7.17.4.1.

7.17 Adverse Events Assessments

7.17.1 Definitions of Adverse Events and Serious Adverse Events

7.17.1.1 Adverse Event

An AE is any noxious, pathologic, or unintended change in anatomical, physiologic, or metabolic function as indicated by physical signs, symptoms, or laboratory changes occurring in a clinical study, whether or not considered investigational product related. This includes an exacerbation of a pre-existing condition. However, any exacerbation or worsening of symptoms of an acute HAE attack treated with icatibant is considered a result of the underlying disease and will not be considered an AE (unless meeting the criteria for a serious adverse event (SAE), see Section 7.17.1.2).

Adverse events include:

- Worsening (change in nature, severity, or frequency) of conditions present at the onset of the study (with the exception of HAE).
- Intercurrent illnesses.
- Drug interactions.
- Events related to or possibly related to concomitant medications.
- Clinically significant abnormal laboratory values (this includes significant shifts from baseline within the range of normal that the investigator considers to be clinically important).
- Clinically significant abnormalities in physical examination, vital signs, and weight.

The investigator must record all AEs in the CRF, regardless of the severity or relationship to investigational product. The investigator should treat subjects with AEs appropriately and observe them at suitable intervals until the events stabilize or resolve. Adverse events may be discovered through observation or examination of the subject, questioning of the subject, complaint by the subject, or by abnormal clinical laboratory values.

In addition, AEs may also include laboratory values that become clinically significantly out of range. In the event of an out-of-range value, the laboratory test should be repeated until it returns to normal or stabilizes, or can be medically explained, and the subject's safety is not at risk.

Additional illnesses present at the time when informed consent is given until the time of treatment are regarded as concomitant illnesses and will be documented on the medical history page of the CRF. Illnesses first occurring or detected on or after treatment, and worsening of a

concomitant illness during the study, are to be regarded as AEs and must be documented as such in the CRF.

The treated HAE attack is defined as any symptoms occurring in treated subjects within 48 hours of the onset of symptoms. A clinically relevant worsening of the signs and symptoms of a treated attack is considered to be related to the underlying disease of HAE, and will be collected in the appropriate CRF separately from general reports of AEs unless meeting the criteria of an SAE. Symptoms reoccurring more than 48 hours after an initial attack will be considered a new attack, and will also not be reported as AEs. Attacks not treated with icatibant will be documented in the appropriate CRF at the Day 90 visit; they are considered to be pre-existing disease and will not be documented as AEs.

Local tolerability will include symptoms at the site of icatibant administration (injection site) and will be assessed separately from general reports of AEs. Injection site reactions will be documented in the “local tolerability” page of the CRF. Injection site reactions that have been reported previously with icatibant included erythema, swelling, burning sensation, itching, warmth and pain and were generally, mild to moderate, transient, and resolved without sequelae. Injection site reactions that do not meet the criteria of an SAE will not need to be additionally reported as AEs.

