7.17.1.2 Serious Adverse Event

An SAE is any AE occurring at any dose that results in any of the following outcomes:

- Death.
- Is life-threatening.
- Requires hospitalization.
- Requires prolongation of existing hospitalization.
- A persistent or significant disability or incapacity.
- A congenital anomaly or birth defect.

Important medical events that may not result in death, be life-threatening, or require hospitalization may be considered an SAE when, based upon appropriate medical judgment, they may jeopardize the subject and may require medical or surgical intervention to prevent one of the outcomes listed in this definition. A life-threatening AE is defined as an AE that placed the subject, in the view of the initial reporter, at immediate risk of death from the AE as it occurred (ie, it does not include an AE that, had it occurred in a more severe form, might have caused death).

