7.17.4.2 Reporting Serious Adverse Events

Any SAE, regardless of relationship to investigational product, which occurs in a subject after informed consent, should be recorded by the clinical site on an SAE form. The SAE must be completely described on the subject's CRF, including the judgment of the investigator as to the relationship of the SAE to the investigational product.

The investigator will promptly supply all information identified and requested by the sponsor (or contract research organization [CRO]) regarding the SAE. The investigator must report the SAE to the Shire Pharmacovigilance and Risk Management Department AND to the Shire Medical Monitor on an SAE form. This form must be completed and faxed or emailed within 24 hours of the investigator's learning of the event to:

Shire Pharmacovigilance and Risk Management Department:

FAX: PPD [redacted] (Worldwide) OR PPD [redacted] (North America)

Email: PPD [redacted]

AND

Shire Medical Monitor: PPD [redacted] MD, MPH

PPD [redacted]

FAX: PPD [redacted] (USA)

Any follow-up information must also be completed on an SAE form and faxed or emailed to the same numbers listed above.

In the event of a severe and unexpected, fatal, or life-threatening SAE, the clinical site must contact the Shire Medical Monitor by telephone; this is in addition to completing and transmitting the SAE form as stated above. The following provides contact information for the Shire Medical Monitor.

If an SAE is assessed as severe and unexpected, or life-threatening, contact:

If an SAE is assessed as severe and unexpected, or life-threatening, contact:

PPD [REDACTED], MD, MPH
PPD [REDACTED]
Shire Orphan Therapies LLC
[name]
[name]
Telephone: PPD [REDACTED]
Mobile: PPD [REDACTED]
Fax: PPD [REDACTED] (USA)
PPD [REDACTED]

The investigator must promptly report all required information to the Institutional Review Board (IRB)/Independent Ethics Committee (IEC). It is the responsibility of the sponsor to ensure that each investigator receives a copy of any Council for International Organizations of Medical Sciences (CIOMS)/MedWatch report that has been submitted to the appropriate regulatory agencies notifying them of an unexpected related SAE.

The investigator or sponsor must ensure that the IRB/IEC receives a copy of the report and that a copy is also filed within their study files.

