7.20.1 Safety-Related Study Stopping Rules

The Data and Safety Monitoring Board (see Section 11.8 for a description of the DSMB and its role) may recommend to suspend the study until the DSMB can review any death that is drug or disease-related or unexplained, or if there is an unexpected drug-related severe AE.

Following the review of safety data, the study will be either:

- Resumed unchanged
- Resumed with modifications to the protocol
- Terminated

Subject safety will be monitored on a continuous basis during this study until the last subject completes his or her last scheduled study visit/assessment.

Additional information on safety monitoring can be found in Section 11.8.

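### Read literally, a serious HAE attack not treated with icatibant has no stated route into 24-hour SAE reporting or the SAP's SAE tables

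*Protocol*

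**What the plan says.** Protocol Section 7.17.1.1 treats HAE symptoms separately from AEs and does so in several steps.

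- **Worsening of an attack treated with icatibant.** It "will not be considered an AE (unless meeting the criteria for a serious adverse event (SAE), see Section 7.17.1.2"). The section later repeats the rule: such worsening "will be collected in the appropriate CRF separately from general reports of AEs unless meeting the criteria of an SAE".
- **A later attack.** "Symptoms reoccurring more than 48 hours after an initial attack will be considered a new attack, and will also not be reported as AEs".
- **An attack not treated with icatibant.** Its place of record is a CRF page at the Day 90 visit. On the status of these attacks the section says: "they are considered to be pre-existing disease and will not be documented as AEs".
- **Injection site reactions.** They are kept off the AE pages unless they meet the SAE criteria.

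Section 7.17.1.2 then defines seriousness: "An SAE is any AE occurring at any dose that results in any of the following outcomes". Section 7.17.4.2 sets the scope of reporting: "Any SAE, regardless of relationship to investigational product, which occurs in a subject after informed consent, should be recorded". It requires the SAE form within 24 hours of the investigator learning of the event, plus a telephone call to the medical monitor for a fatal or life-threatening SAE. Section 7.20.1 lets the DSMB recommend suspending the study so that it can "review any death that is drug or disease-related or unexplained".

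**The concern.** The seriousness exception is written out for two of the excluded event types and left out for the other two. A site may reasonably take the omission as deliberate. The omitted types include the events that Protocol Section 1.1 describes as the gravest risk of the disease: laryngeal attacks, with possible death by asphyxiation, which may develop faster in children than in adults.

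At stake is the speed and completeness of safety reporting in a paediatric study. If the text is applied as written, an untreated attack that leads to hospitalisation or death could go to a routine CRF page or a scheduled call. It would not go on an SAE form within 24 hours. It could then be missing from the SAE summaries in the study report.

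**Working it through.** No plan figure needs reproducing. The check sets the sections side by side.

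**1. Which exclusions carry a seriousness exception (Protocol Section 7.17.1.1)**

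| Event | Kept out of AE reporting | Exception if serious |
|---|---|---|
| Worsening of a treated attack | Yes | Yes, stated twice |
| Injection site reaction | Yes | Yes |
| New attack, more than 48 hours on | Yes | None in the sentence |
| Attack not treated with icatibant | Yes | None |

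The bulleted list of AE types in the same section also exempts worsening of HAE, with no exception.

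**2. From AE to SAE.** Under Section 7.17.1.2 an SAE is an AE with a listed outcome. An event that is never an AE therefore cannot, on the words, become an SAE.

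**3. From SAE to the 24-hour report.** The form and the telephone call in Section 7.17.4.2 both attach to SAEs. The phrase about relationship there removes a causality filter. It does not remove the condition in step 2.

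**4. Who falls in the gap**

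- Prepubertal subjects after their single dose (Section 6.2). At least 10 of the 30 planned subjects are prepubertal, and none of their later attacks can be treated on study.
- Early recurrences. Section 6.3 allows re-treatment only from 3 days after the prior treatment. Take 3 days as 72 hours after the dose, and count the 48 hours from symptom onset, as the treated-attack definition does. With dosing 0 to 12 hours after onset, the 48-hour point falls 48 − 0 = 48 to 48 − 12 = 36 hours after the dose. The interval in which symptoms count as a new attack but cannot receive study icatibant is then 72 − 48 = 24 to 72 − 36 = 36 hours long. If the 48 hours are counted from the end of the attack, it is shorter or absent.
- Pubertal/postpubertal subjects who have had all 3 permitted doses.
- Subjects between consent and first dose. Section 4.3 describes an open-ended wait for those who are to be dosed during an attack.

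A new attack that is treated with icatibant on study is a treated attack, so worsening that meets SAE criteria is covered again.

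**5. Other capture.** Untreated attacks are recorded at Day 90 (Section 8.3.3), at 6-monthly telephone contacts (Section 8.1) and at a monthly safety call for subjects who remain enrolled (Section 4.1.3.2). The monthly call is scheduled only in Appendix 3. None of these is expedited.

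**6. Analysis outputs.** SAP Section 7.9.1 counts deaths as AEs resulting in death. Tables 14.3.5.1 to 14.3.5.3 and Listing 16.2.7.5 are built from SAEs. No table or listing title in SAP Appendix I names attacks not treated with icatibant. An event stopped at step 2 could be missing from all of these outputs.

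**7. The DSMB.** Section 7.20.1 covers disease-related deaths and does not require AE or SAE status. A fatal attack is inside that wording. The documents do not state how news of it would promptly reach the sponsor and the DSMB if no SAE form is sent.

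**The case against.** The strongest reply is that the protocol does not use the SAE definition as a barrier. It takes events that are not AEs and makes them reportable when serious, and it collects SAEs from consent although AEs are collected only from treatment. SAP Listing 16.2.7.5 covers SAEs in all subjects. On this view seriousness always overrides the exclusion, and a careful investigator would report. That is probably the intent. But each override is written out where it applies, and the sentence on untreated attacks has none.

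For new attacks the reply is stronger. The word also in that sentence can be read as carrying over the exception just stated, and many such attacks in pubertal/postpubertal subjects can be treated on study. This half of the point is therefore ambiguous.

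A further reply is that Protocol Section 1.2.2 reports the initial-treatment component as complete. That limits what an amendment can still change for prepubertal subjects. It does not settle how their events are tabulated.

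A reader might also infer more than the documents support:

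- **That a fatal attack lies outside the DSMB's trigger.** Section 7.20.1 names disease-related deaths whatever their AE status.
- **That nearly all of the 90-day follow-up lacks the exception.** A share of calendar time is not a share of events, and each later treated attack opens a new period with the exception.
- **That an untreated attack would stay unknown until Day 90, or that rebound could not be seen.** After the initial treatment there are contacts at 24 and 48 hours and a Day 8 visit. Monthly calls are stated for enrolled subjects, and untreated attacks go on the CRF. Rescue medication is assessed through 48 hours, and the SAP summarises concomitant medication within 5 days of dosing.

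**Conclusion.** The point holds as a defect in the reporting rules. For attacks not treated with icatibant, the protocol excludes AE reporting without a seriousness exception, and its SAE definition then keeps a serious attack out of the 24-hour report. For new attacks more than 48 hours on, the same follows less clearly. The fault affects the timing of reporting and the completeness of the SAE outputs. It does not affect the DSMB's authority to review a death.

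The size is given by the groups listed in the working, not by a number of events, because the documents give no rate of serious untreated attacks. The conclusion assumes that sites apply the text as written. It also assumes that documents not supplied, such as the DSMB charter and the CRF instructions, do not already close the gap. The point should be corrected despite the uncertain frequency, because these are potentially fatal events in children and the remedy is short.

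**What to change.** In Protocol Section 7.17.1.1, add to the sentence on new attacks and to the sentence on attacks not treated with icatibant the exception already given for worsening of a treated attack. Point it to Section 7.17.1.2 for the criteria and to Section 7.17.4.2 for reporting. State how a death from HAE reaches the sponsor and the DSMB promptly for Section 7.20.1.

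In the SAP, state that these events enter Listing 16.2.7.5 and, if they occur after the first dose, the treatment-emergent SAE tables. State also that a fatal one is included in the count of AEs resulting in death. For subjects whose follow-up is already over, check the recorded untreated attacks for any that met a seriousness criterion.

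The cost is two clauses, a short SAP statement and a notice to sites. The downside is a few more SAE reports, probably judged unrelated, and so a slightly higher SAE count.

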7.17.1.2 Serious Adverse Event

An SAE is any AE occurring at any dose that results in any of the following outcomes:

- Death.
- Is life-threatening.
- Requires hospitalization.
- Requires prolongation of existing hospitalization.
- A persistent or significant disability or incapacity.
- A congenital anomaly or birth defect.

Important medical events that may not result in death, be life-threatening, or require hospitalization may be considered an SAE when, based upon appropriate medical judgment, they may jeopardize the subject and may require medical or surgical intervention to prevent one of the outcomes listed in this definition. A life-threatening AE is defined as an AE that placed the subject, in the view of the initial reporter, at immediate risk of death from the AE as it occurred (ie, it does not include an AE that, had it occurred in a more severe form, might have caused death).

7.17.2 Classification of Adverse Events and Serious Adverse Events

The severity of AEs will be assessed by the investigator as mild, moderate, or severe based on the definitions shown in [Table 7-2](#). The severity of AEs and SAEs should be recorded on the appropriate CRF page as mild, moderate, or severe.

Table 7-2 Adverse Event Severity

Severity	Definition
Mild	No limitation of usual activities.
Moderate	Some limitation of usual activities.
Severe	Inability to carry out usual activities.

7.17.2.1 Clarification between Serious and Severe

The term “severe” is often used to describe the intensity (severity) of a specific event (as in mild, moderate, or severe myocardial infarction); the event itself, however, may be of relatively minor medical significance (eg, severe headache). This is not the same as “serious,” which is based on the outcome or action criteria usually associated with events that pose a threat to life or functioning. Seriousness (not severity) and causality serve as a guide for defining regulatory reporting obligations.

